5.6.2 DOSING AND ADMINISTRATION

See above Table for Aim 2

5.7 PREPARATION/HANDLING/STORAGE/ACCOUNTABILITY

5.7.1 ACQUISITION AND ACCOUNTABILITY

The investigator will obtain the Dexcom G6 CGM packages from the manufacturer and will provide it to all patients at no charge, as part of the study by the study team (PI, Co-PIs, Coordinators). After removal, data download, and stored, devices will be discarded following standard precautions.

Investigational Device	Total # returned to Site	Total # Used	Total # Used and Returned	Total # Unused and Returned
CGM Sensors: Lot #:				
Reader:				

5.7.2 FORMULATION, APPEARANCE, PACKAGING, AND LABELING

The following performance specifications of the CGM System are applicable to the study:

Sample type:	Interstitial Fluid
Test sites:	Abdominal area (above beltline) and back of upper arm
Calibration requirements:	Not required
Wear use Life:	Up to 10 days
Range of measurement:	40-400 mg/dL
Humidity Range:	10-95% relative humidity
Altitude:	Up to 13,800 feet
CGM Sensor Useful Life:	3 months
Measured Parameter:	Interstitial Fluid Glucose

Packaging Information

Product Name
Catalog #
Lot #
Expiration Date
Date of Manufacture
Serial Number
Unique Device Identifier
Name and Address of Manufacturer

5.7.3 PRODUCT STORAGE AND STABILITY**Storage**

Keep in its sterile packaging until you're ready to use it.
Store at temperatures between 36° F and 77° F.
Storing outside this range may cause inaccurate G6 readings.
May store sensor in refrigerator if it's within temperature range.
Store sensors in a cool, dry place. Don't store in parked car on a hot day or in freezer.

Transmitter

Keep protected when not in use
Store at temperatures between 32° F and 113° F
Store between 10% and 95% relative humidity

Receiver

Keep protected when not in use
Fully charge the battery before storing for over 3 months
Store at temperatures between 32° F and 104° F
Store between 10% and 95% relative humidity

5.7.4 PREPARATION**Installation of the CGMs:**

The steps involved with the installation of the CGMs are as follows:

1. Participant will go to a private area
2. Study staff will clean your skin using an alcohol wipe and allow it to air dry.
3. The area of insertion will be shaved if clinical study staff determines that this is needed, you can use a shaving method of your choice. You may bring your own razor or electric shaver, or we will provide a disposable razor for you.
4. The study team will remove the CGM and Inserter Assemblies from their packaging.
5. The staff member will remove the adhesive backing from each Inserter Assembly. The adhesive backing is similar to the adhesive backing of a bandage.
6. The staff member will place each Inserter Assembly against your skin surface at the selected insertion site.
7. The staff member will then gently push down on the Inserter Assembly until he/she hears and feels a "Click" indicating the CGM has been inserted below the skin surface. At the time of CGM insertion you will feel a small prick similar to the insertion of a small needle.

8. The staff member will then gently remove the Inserter Assembly from the CGM leaving behind the CGM attached to your skin surface.
9. The staff member will then verify proper insertion and adhesion of the CGM to the skin surface.
10. Lastly, the staff member will explain the benefit of using a protective Overpatch over each of the CGMs for the duration of the study to prevent water damage and ensure adhesion to the attachment site. The decision to use a protective Overpatch will be your decision and is not a requirement of the clinical study.

If additional insertions are required in the event of an immediate CGM failure or failure that occurs during the study period, we will not attempt more than two (2) CGM insertions during the study period.

Once the CGMs have been successfully installed, the staff member will synch the internal Transmitters to two (2) Readers provided. Each Reader is used to display your interstitial blood glucose (sugar) values to you continuously.

The newly installed CGMs will take about 60 minutes to equilibrate after installation. During this time the staff members will prepare you for your first clinical study visit.

5.8 MEASURES TO MINIMIZE BIAS: RANDOMIZATION AND BLINDING

Aim 2. RCT

Subjects will be randomly allocated to each study phase using a computer-generated randomization scheme provided by [name], Professor of Biostatistics. Subjects will be randomized by prior history of hypoglycemia (reported or on blinded CGM). One research member not included in our team will maintain the randomization table. Due to the nature of the intervention (e.g. real-time CGM data vs POC BG), this will be an open label RCT. However, subjects and investigator will have no real-time/direct access to the primary outcome data (percentage of time in hypoglycemic range) until completion of the study, and after the CGM data is downloaded. Investigators and study team will be masked until completion of all study phases are completed, and the large CGM dataset is analyzed.

5.9 STUDY INTERVENTION COMPLIANCE

Criteria for participants to continue with randomization are 1) willingness and ability to use the CGM device, 2) and CGM adherence, defined as a minimum of 70% usage (e.g. at least 7 days of CGM readings). The CGM data will NOT be shared with participants, clinicians at the research site, or the treating community clinician.

It is possible that sensors fall off, thus we will cover the sensor with Tegaderm Adhesive Films. In our practice, this decreases the fall off rate to <10%. Sensors that fail within the first 24 hours will be replaced, and the study will start again on Day 1 after insertion (replacement up to 2 times).

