maintenance hemodialysis¹⁵. Moreover, the POC BG approach fails to detect asymptomatic and nocturnal hypoglycemia and fails to provide a complete glycemic profile throughout the day, particularly during dialysis sessions¹⁶. Hence, there is a critical need to find a standardized long-term outcome measure for glycemic control in dialysis patients, but also a glycemic measure that will allow patients and clinicians make rapid therapeutic decisions to prevent hypoglycemia^{3,17}. New diabetes technology devices, such as continuous glucose monitoring (CGM), have the potential to become the new standard of care for assessment of glycemic control in dialysis patients; however, there are no studies assessing the efficacy and safety of the novel-factory calibrated sensors in this population.

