A3. Management of Dysglycemia in Patients on Hemodialysis. Most anti-diabetic drugs require dose adjustments or are contraindicated in patients with advanced CKD or ESRD^{3,4,7}. Thus, ~60-70% of patients with type 2 DM on hemodialysis are managed with insulin therapy¹⁸⁻²⁰, or with a combination of insulin and oral agents (sulfonylureas) which are associated with increased risk of adverse events²⁰. In our institution, 56% of patients with type 2 DM are currently treated with insulin therapy, 37% received no therapy, and 7% are treated with oral agents: 40% secretagogues and 60% incretins. Notably, treatment with insulin and/or sulfonylureas is associated with a higher risk for emergency department (ED) visits and hospitalization for hypoglycemia among patients with ESRD²⁰. In addition, hypoglycemia is associated with increased risk of cardiac arrhythmias²¹, strokes²², seizures²³, and sudden cardiac death^{23,24}. Nevertheless, the evidence on the association between hypoglycemia and different anti-diabetic agents is limited^{20,25}. In a small study (n: 10) of patients with type 2 diabetes and ESRD, Sobngwi et al. analyzed insulin needs during a euglycemic clamp and using short-term retrospective CGM¹⁶. The authors demonstrated that basal insulin doses decreased by 25% post-hemodialysis, compared to the pre-dialysis day. In a similar study using CGM, but in patients with no diabetes and ESRD, the same group reported a tendency towards lower glucose during the hemodialysis sessions, with a nadir at the 3rd hour²⁶. However, no prospective intervention study has been performed using CGM to adjust insulin therapy in ESRD patients. We hypothesize that the high risk of hypoglycemia in this population relates to the high insulin and sulfonylurea utilization and to poor treatment dose adjustments due to lack of reliable glucose monitoring data to guide therapy.

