2.3 RISK/BENEFIT ASSESSMENT

2.3.1 KNOWN POTENTIAL RISKS

1.a. Patients who develop hypoglycemia: We anticipate that ~50% of individuals recruited for this study will develop hypoglycemia by POC BG (as available).

During the observation study, blinded CGM data will be collected. Thus, subjects will be instructed to perform POC BG, as standard of care, for glucose monitoring. The study team will provide subjects with training on hypoglycemia management and prevention. If the study subject experiences hypoglycemic symptoms during the dialysis/blood glucose testing, we will notify the dialysis team to check a blood glucose and treat per standard of care. If POC BG or -YSI glucose is < 70 mg/dl, subjects will be given corrective measures, per standard of care, and communicate to their treating physician regarding subject's insulin doses and the need for follow-up for treatment of diabetes.

During the interventional study, all subjects will receive standard guidelines on how to adjust insulin based on CGM or POC BG data, and how to treat hypoglycemia per standard of care. The sensors provide a predictive hypoglycemia alarm ("predictive urgent low soon") that will alarm the subject within the preceding 20 minutes of a glucose < 55 mg/dl. The main objective of our RCT is to prevent hypoglycemia.

1.b. Risk of hyperglycemia.

We will exclude subjects with severe hyperglycemia (BG > 400 mg/dl) during consent/randomization. These subjects will be notified of the findings and advise to communicate with their treating physician for treatment adjustments.

1.c. Phlebotomy: Risks associated with phlebotomy and IV insertion are low and include small amounts of pain, possible bruising, swelling, redness, and rarely an infection at the site. However, we will collect blood from the pre-dialysis circuit and after the dialysis nurse inserted the dialysis needle. Approximately, ~5-10 ml of blood will be obtained during the dialysis for glucose testing (Aim 1b). These risks will be shared with the participants during informed consent and before starting the studies.

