Investigator, would interfere with their participation in the trial (e.g., marked visual or hearing impairment, active alcohol or drug abuse, mental illness) or pose excessive risk to study staff handling venous blood samples. Situations that will limit the subject's ability to comply with the protocol (per investigator discretion), active malignancy, unable to give informed consent, at least 10% of time spent in clinical relevant hypoglycemia (<54 mg/dl) during blinded CGM period, significant hypoglycemia (< 40 mg/dL) or severe hyperglycemia (BG > 400 mg/dL) during randomization, extensive skin abnormalities at insertion sites, pregnancy or breastfeeding, severe anemia (Hemoglobin < 5 mg/dl) or polycythemia (Hemoglobin >17 mg/dl), subjects taking acetaminophen (more than 1 gr every six hours) or hydroxyurea (may cause interference with the sensor membrane).

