5.10 CONCOMITANT THERAPY

For this protocol, a prescription medication is defined as a medication that can be prescribed only by a properly authorized/licensed clinician. Medications to be reported in the Case Report

Form (CRF) are concomitant prescription medications, over-the-counter medications and supplements. The study will not provide any study medications. Treatment will be determined by the treating physician.

For Aim 1, we will include subjects on dialysis treated with insulin therapy [basal insulin alone (glargine U100, glargine U300, detemir, degludec, NPH)], or in combination with bolus insulin (at least one or more injections of aspart, lispro, glulisine, regular insulin) or in combination with incretin therapy (i.e. DPP4 inhibitors or GLP1 agonists). Subjects taking hydroxyurea (may cause interference with the sensor membrane), taking secretagogues (glipizide, glyburide, glimepiride, repaglinide).

For Aim 2, subjects treated with insulin therapy [basal insulin alone (glargine U100, glargine U300, detemir, degludec, NPH)], or in combination with bolus insulin (at least one or more injections of aspart, lispro, glulisine, regular insulin) or in combination with incretin therapy (i.e. DPP4 inhibitors or GLP1 agonists). Subjects using sulfonylureas or thiazolidinediones alone or in combination with insulin. Use of personal/real-time CGM 3 months prior to study entry (blinded CGM is allowed), prior use of insulin pumps or hybrid close loop systems (for at least the prior 28 days), current or anticipated use of stress steroids doses (prednisone \leq 5mg or its equivalent is allowed

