8.2 SAMPLE SIZE DETERMINATION

No preliminary data is available on ESRD patients with this device. Heinemann et al.⁴² studied subjects with hypoglycemia treated with insulin. The authors reported medians and interquartile ranges of this outcome under RT-CGM or usual care. Based on these preliminary data, we approximated the standard deviation (SD) of our primary outcome under the normality assumption. This suggests 6.45% as a conservative upper bound for the SD. Assuming 10% attrition rate and 6.45% as the SD of the primary outcome, recruiting 45 subjects would give 90% power to detect a mean difference in percentage time in hypoglycemia range which equals 4.8%, based on a two-sided t-test for a two by two cross-over design, with alpha=0.05.

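### Nothing visible in the plan provides for telling a person excluded from Aim 2 for prolonged run-in hypoglycaemia, or their physician, and section 5.9 as worded withholds the data

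*Combined protocol and SAP*

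**What the plan says.** Section 5.2 lists among the Aim 2 exclusions "at least 10% of time spent in clinical relevant hypoglycemia (<54 mg/dl) during blinded CGM period". Under section 5.6.1 the blinded sensor is worn for 10 days, then removed and downloaded at the randomization visit. The schedule of activities shows eligibility being rechecked at that visit (V2).

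Section 5.9 gives the conditions for continuing to randomization, including at least 70% sensor use, for example 7 days of readings. It then states: "The CGM data will NOT be shared with participants, clinicians at the research site, or the treating community clinician". No exception follows.

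Section 2.3.1 has two provisions for out-of-range glucose that lead to the treating physician:

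- Item 1.b concerns people excluded for a blood glucose above 400 mg/dL: "These subjects will be notified of the findings and advise to communicate with their treating physician for treatment adjustments".
- Item 1.a, in its paragraph on the observational study, applies when a POC or YSI value is "< 70 mg/dl, subjects will be given corrective measures, per standard of care, and communicate to their treating physician".

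On who manages the diabetes, section 5.10 says: "Treatment will be determined by the treating physician".

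**The concern.** The plan uses the blinded run-in to find people with so much time below 54 mg/dL that they should not be randomized. It then makes no visible provision for that finding to reach anyone who could act on it. The treating physician, who decides the insulin dose, is one of the parties from whom 5.9 withholds the data.

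The protocol itself describes what is at stake. Section 2.2 (A3) says that "hypoglycemia is associated with increased risk of cardiac arrhythmias" and goes on to name stroke, seizure and sudden cardiac death. Self-monitoring during the run-in cannot be relied on to reveal the problem, because section 2.2 (A2) says that "the POC BG approach fails to detect asymptomatic and nocturnal hypoglycemia". The hypoglycaemia training at V1 is general and does not tell a person that they had hypoglycaemia.

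The contrast with high glucose sharpens the point. The plan already tells people excluded for a dangerously high value, and it omits the same step for this low-glucose exclusion. Item 1.a of section 2.3.1 gives preventing hypoglycaemia as the main aim of the randomized trial.

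**Working it through.** The plan states no figure to reproduce here. The check compares the sections and then converts the exclusion threshold into time.

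**Is there a notice anywhere for this exclusion?**

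| Section | What it provides | Covers a run-in CGM hypoglycaemia exclusion? |
|---|---|---|
| 2.3.1, item 1.b | Notice and referral for blood glucose >400 mg/dL | No: high glucose only |
| 2.3.1, item 1.a, observational study | Correction and contact with the physician when POC or YSI is <70 mg/dL | No: triggered by meter or YSI, not by CGM |
| 5.4 | Definition of screen failure, rescreening, run-in extension | No notification step |
| 5.8 | Masking of time-in-hypoglycaemia data until completion | No: restricts access |
| 5.9 | CGM data not shared with participant, site clinicians or treating clinician | No: as worded, bars it |
| 7.3.6 | Reporting events to participants: marked as not applicable | No |
| 7.4.2 | Individual notice of unanticipated problems | No: those problems only |

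**Does the result depend on how 5.9 is read?** There are two readings.

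1. If 5.9 covers everyone in the run-in, it bars giving the information.
2. If 5.9 covers only those who continue to randomization, nothing bars the notice, but nothing provides for it either.

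The gap exists on both readings.

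**How much hypoglycaemia does the threshold represent?** The inputs are 10% of time (5.2), 1,440 minutes per day, at least 7 days of readings (5.9) and a 10-day run-in (5.6.1).

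- Per day: 0.10 × 1,440 = 144 minutes below 54 mg/dL.
- Over 7 full days of readings: 144 × 7 = 1,008 minutes = 16.8 hours.
- Over 10 full days: 144 × 10 = 1,440 minutes = 24 hours.

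These are lower bounds for anyone who meets the criterion.

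**A yardstick from the plan.** Section 8.2 sizes Aim 2 on "a mean difference in percentage time in hypoglycemia range which equals 4.8" percent, with the range defined as below 70 mg/dL.

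- 0.048 × 1,440 = 69.1 minutes per day.
- 144 / 69.1 = 2.08.

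The exclusion threshold is thus about 2.1 times that share of time, at a lower glucose cut-off. One figure is a between-treatment mean difference and the other an individual cut-off, so the ratio gives scale only and does not measure harm.

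**The case against.** The strongest reply is that 5.9 is really a masking rule. It follows the conditions for continuing to randomization. Read literally it would even keep participants from their own real-time CGM, which is the intervention, so the literal reading cannot be the intended one. That is fair as to intent. It leaves the text without a notice, however, and an investigator who follows 5.9 literally would still withhold the data.

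Second, the existing notices act on blood values, and section 2.2 says factory-calibrated CGM had not been studied in ESRD. Declining to act on CGM could therefore be deliberate. Against this, the plan trusts the same CGM data enough to exclude a person.

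Third, other safeguards exist: four-times-daily self-monitoring as available, possible exclusion for not self-monitoring, V1 training and, for people entering from Aim 1, contact with the physician after a low POC or YSI value. These narrow the gap, mainly to lows seen only on CGM and to people who enter Aim 2 directly. None of them discloses the CGM finding.

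Fourth, the consent form and the manual of procedures are not available here and could contain a provision. That cannot be excluded, and the conclusion is limited to the visible text. A provision there would still conflict with 5.9 as worded if 5.9 applies to excluded people.

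Finally, no effect on randomized participants or on the primary analysis is claimed. That is correct: this is a participant-safety omission and does not affect the validity of the estimate.

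**Conclusion.** The concern holds and should be fixed. In the visible plan, a person excluded for at least 10% of run-in time below 54 mg/dL has no assured route to learning of it, and neither does their physician. Section 5.9 as worded points the other way. Such a person has spent at least 16.8 hours (7 days of readings) to 24 hours (10 days) below 54 mg/dL.

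The hour figures assume complete readings on each counted day. The documents give no expected number of such exclusions, and none is assumed here; it could be zero. The conclusion does not depend on which reading of 5.9 is adopted.

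**What to change.** Add an exception to 5.9, with matching text in 2.3.1, item 1.a:

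> A person excluded from Aim 2 because of at least 10% of time <54 mg/dL in the blinded run-in will be told the reason and advised to contact their treating physician for treatment adjustment, as for BG >400 mg/dL.

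Keep the no-sharing rule for participants who continue, preferably limited explicitly to blinded CGM data so that it does not contradict the real-time phase. Optionally, add a sentence allowing the study team to review the run-in download for eligibility and for the hypoglycaemia-history stratum in 5.8. Someone has to read those data to apply the exclusion.

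The cost is one sentence in two places and a short conversation with each person concerned. Nobody randomized is affected, and neither is the primary outcome, which section 8.1 takes from the final 10 days of each phase. Section 5.4 allows rescreening only after acute illness, a hospital stay or a temporary break in dialysis, so it gives a person informed in this way no route back into the trial.

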5.10 CONCOMITANT THERAPY

For this protocol, a prescription medication is defined as a medication that can be prescribed only by a properly authorized/licensed clinician. Medications to be reported in the Case Report

Form (CRF) are concomitant prescription medications, over-the-counter medications and supplements. The study will not provide any study medications. Treatment will be determined by the treating physician.

For Aim 1, we will include subjects on dialysis treated with insulin therapy [basal insulin alone (glargine U100, glargine U300, detemir, degludec, NPH)], or in combination with bolus insulin (at least one or more injections of aspart, lispro, glulisine, regular insulin) or in combination with incretin therapy (i.e. DPP4 inhibitors or GLP1 agonists). Subjects taking hydroxyurea (may cause interference with the sensor membrane), taking secretagogues (glipizide, glyburide, glimepiride, repaglinide).

For Aim 2, subjects treated with insulin therapy [basal insulin alone (glargine U100, glargine U300, detemir, degludec, NPH)], or in combination with bolus insulin (at least one or more injections of aspart, lispro, glulisine, regular insulin) or in combination with incretin therapy (i.e. DPP4 inhibitors or GLP1 agonists). Subjects using sulfonylureas or thiazolidinediones alone or in combination with insulin. Use of personal/real-time CGM 3 months prior to study entry (blinded CGM is allowed), prior use of insulin pumps or hybrid close loop systems (for at least the prior 28 days), current or anticipated use of stress steroids doses (prednisone \leq 5mg or its equivalent is allowed

5.10.1 RESCUE MEDICINE

The study will not supply rescue medication. Insulin doses will be adjusted during the trial.

6 STUDY INTERVENTION DISCONTINUATION AND PARTICIPANT DISCONTINUATION/WITHDRAWAL

6.1 DISCONTINUATION OF STUDY INTERVENTION

Participation in the clinical study will be terminated for each participant following the last visit or when all AEs have been resolved or considered ongoing but stable. Prior to this time, participants may voluntarily withdraw at any point in the study or the Investigator and/or Sponsor may determine that it is in the best interest of the participant to be terminated from the study.

Reasons for withdrawal of participant from the study include, but are not limited, to the following:

- a) In the opinion of the Investigator, the participant's health or safety would be compromised by continuing in the study
- b) In the opinion of the Investigator, it is in the participant's best interest to discontinue participation in the study
- c) During the study, (female) participant becomes pregnant

However, discontinuation of the study intervention (CGM) does not equate with discontinuation from the study and every effort will be made to retain participants in the study for the primary outcome assessment, even if CGM is discontinued.

The clinical study in its entirety will be considered complete upon receipt of reports from study monitoring activities, completion of site closeout visits, and issuance of a clinical study report. The clinical study report will include all safety and efficacy data.

Insertion of the CGM sensor will be performed per manufacture instructions and following an aseptic technique. After insertion of the sensors, providers will ensure proper hemostasis is achieved. Sensors will be removed if prolonged bleeding or severe pain occurs.

